8.2. Treatment Assignment

All subjects who meet the eligibility criteria as per 9.2 and 9.3 and sign the informed consent will be considered enrolled. Data will be collected during the baseline visit, the ablation (index) procedure, the pre-discharge visit, the month 3assessment and during the month 4 follow up. In case additional visits or additional ablation procedures take place, this data will also be collected. Please refer to Section 11.2 to 11.10 for an overview of data to be collected during these visits.

A study subject can only be enrolled once in the study.

8.2.1. Treatment and Control

For all enrolled subjects who undergo the ablation procedure, the subjects will be treated with the commercial Rhythmia HDx System with commercially available Software Version 2.0 with DirectSense technology (or any commercially available updates that are released during the course of the study), the IntellaMap Orion mapping catheter and the IntellaNav MiFi OI ablation catheter. Initial encircling of the PVs will be performed by Investigators who perform the ablation blinded with respect to DirectSense (single blind masking). This will not impact the AE assessment by the investigator.

8.3. Justification for the Study Design

This is a post-market study designed to collect specific information in order to characterize the DirectSense technology in subjects undergoing catheter-based endocardial mapping and ablation for de-novo PAF using a commercial Rhythmia HDx mapping system. The DirectSense feature generates local impedance data that is automatically stored in the Rhythmia HDx mapping system during PVI. In this study local impedance data will be retrieved from the system for off-line analysis. As Direct Sense is intended to provide information on the localization of the ablation catheter to cardiac tissue (and the ability to create durable PV lesions), an additional endocardial mapping procedure at 3 month is required in this study in order to assess gaps in the PV, after substrate stabilization. This information will be used to evaluate the association between impedance readings at initial PVI and a durable isolation at 3 months (primary endpoint). This month 3 assessment is not standard of care in clinical practice, but a recognized standard for clinical studies and literature in order to verify durable isolation of PV (acute assessment is unable to detect mid-term gaps). Subjects will be followed at month 4 for patient status/AE assessment.

9. Subject Selection

9.1. Study Population and Eligibility

Subjects enrolled in the LOCALIZE study will be clinically indicated for an endocardial catheter-based mapping procedure for the treatment of de-novo PAF and meet the study inclusion/exclusion criteria as outlined below in section 9.2 and 9.3. The subjects selected for participation will be from the investigator's general patient population. The investigator or its designee has the responsibility for screening all potential subjects and selecting those who meet study inclusion/exclusion.

9.2. Inclusion Criteria

Subjects who meet all of the following criteria (see **Table 9.2-1**) may be given consideration for inclusion in this clinical investigation, provided no exclusion criterion (see Section 9.3) is met.

Table 9.2-1: Inclusion Criteria

	-
Clinical Inclusion Criteria	 History of recurrent symptomatic PAF with ≥1 episode reported and documented within the 365 days prior to enrollment; PAF is defined as AF episodes that last ≥30 seconds in duration and terminate within 7 days.
	• Refractory or intolerant to at least one Beta Blocker, Calcium Channel Blocker, Class I OR Class III anti-arrhythmic drug (AAD);
	• Eligible for an ablation procedure with the Rhythmia HDx mapping system (software version 2.0 or any future commercially available Software Version), IntellaMap Orion mapping catheter and IntellaNav MiFi OI ablation catheter according to current international and local guidelines (and future revisions) and per physician discretion;
	Subjects who are willing and capable of providing informed consent;
	 Subjects who are willing and capable of participating in all testing associated with this clinical investigation at an approved clinical investigational center;
	• Age 18 to 80

9.3. Exclusion Criteria

Subjects who meet any one of the following criteria (**Table 9.3-1**) will be excluded from this clinical study.

Table 9.3-1: Exclusion Criteria

Clinical Exclusion Criteria

- Diagnosed with any of the following heart conditions within 90 days (3 months) prior to enrollment:
 - a. New York Heart Association (NYHA) Class III or IV
 - b. Left ventricular ejection fraction (LVEF) <35%
 - c. Left atrial (LA) diameter >5.5 cm
 - d. Unstable angina or ongoing myocardial ischemia (OMI)
 - e. Transmural myocardial infarction (MI), acute coronary syndrome (ACS), percutaneous coronary intervention (PCI), or valve or coronary bypass grafting surgery
- Active systemic infection or sepsis;
- Undergone any left atrial heart ablation procedure, either surgical or catheter ablation
- Prosthetic or stenotic valves in the chamber where the intended mapping will occur, or in the path of the catheter access route
- Subject has a Left Atrial Appendage Closure (LAAC) or Percutaneous Transcatheter Closure of a Patent Foramen Ovale (PFO)
- Subject has persistent or long-standing persistent atrial fibrillation (AF) (>1 AF episodes lasting greater than 7 days, with no episodes having lasted greater than 30 days, within the past year)
- Life expectancy ≤ 6 months per physician judgment
- Subjects who are currently enrolled in another investigational study or registry that would directly interfere with the current study, except when the subject is participating in a mandatory governmental registry, or a purely observational registry with no associated treatments; each instance must be brought to the attention of the sponsor to determine eligibility;
- The subject is unable or not willing to complete follow-up visits and examination for the duration of the study;
- Women of childbearing potential who are, or plan to become, pregnant during the time of the study (method of assessment upon physician's discretion).

10. Subject Accountability

10.1. Point of Enrollment

Subjects who meet the eligibility criteria and have signed and dated the Informed Consent Form are considered enrolled in the study. No further review of eligibility criteria for study participation is required beyond this point. It is the investigator's site responsibility to assess eligibility criteria before the index procedure.

10.2. Withdrawal

All subjects enrolled in the clinical study (including those withdrawn from the clinical study or lost to follow-up) shall be accounted for and documented. If a subject withdraws from the clinical investigation, the reason(s) shall be reported. If such withdrawal is due to problems related to study device safety or performance, the investigator shall ask for the subject's permission to follow his/her status/condition outside of the clinical study.

Every effort should be made to retain subject enrollment for the duration of the study. During the informed consent process, subjects should be fully informed of the data collection requirements and duration, and should only be enrolled if willing to fully participate in it.

Reasons for withdrawal may include physician discretion, subject choice to retire consent, lost to follow-up, or death. In the event a subject does decide to withdraw from the study, every effort should be made to obtain full information on any on-going reportable Adverse Events up to the point of withdrawal. Subjects should only be considered lost to follow-up after significant effort has been made to contact the subject. For subjects who are "lost-to-follow-up" the investigator/center should have at least three documented attempts to contact the subject prior to completion of the "End of Study" eCRF. Subject withdrawal and lost to follow-up will be documented on the "End of Study" electronic Case Report Form (eCRF). Additional data may no longer be collected after the point at which a subject has been withdrawn from the study or withdraws his/her consent, for whatever reason.

All open reportable Adverse Events should be closed or documented as chronic. Data collected up to the point of subject withdrawal may be used, unless any local regulations apply which require removal of the data.

10.3. Subject Status and Classification

As subjects are evaluated, enrolled and treated in the study, they will be grouped into one of the following several categories. Categorization will help determine how data gathered from them will be stored and evaluated.

Consent Ineligible

A subject who has signed informed consent but does not meet eligibility criteria will be classified as "Consent Ineligible". There are no Follow Up reporting requirements for

PM007 Confidential

Form/Template 90702637 Rev/Ver AH LOCALIZE protocol, document 92142978, Rev/Ver AB Page 27 of 65

consent ineligible subjects. Subjects determined to be Consent Ineligible according to statements above do not count towards the enrollment ceiling and will not be used for analysis of the endpoints. The original signed Informed Consent must be maintained in the center's patient file. A subject Identification Number (ID) is created by Medidata Rave upon entering the subject in the eCRF. For consent ineligible subjects, an enrollment eCRF (ICF form and in-and exclusion criteria forms) and "end of study" eCRF form must be completed. If applicable, an Adverse Event eCRF form must be completed.

Intent

A subject who signs informed consent, meets eligibility criteria, but withdraws or is withdrawn prior to starting the encircling of the 4 PVs (prior to the 1st RF application in the left atrium) will be classified as "INTENT". Subjects that are enrolled in the study but do not undergo ablation procedure within 60 days from consent signature date are withdrawn from the study and classified as "INTENT".

There are no Follow Up requirements for Intent subjects. Intent subjects do not count towards the enrollment ceiling and will not be used for analysis of the endpoints. The original signed Informed Consent must be maintained in the center's patient file. A subject ID is created by Medidata Rave upon entering the subject in the eCRF. For intent subjects, an enrollment, baseline and "end of study" eCRF form must be completed. If applicable, an Adverse Event eCRF form must be completed. No index procedure eCRF must be completed.

Attempt

A subject who signs informed consent, meets eligibility criteria and had the encircling of the 4 PVs started (post the 1st RF application in the left atrium), but did not have the initial encircling for all 4 PVs (2 PV pairs) completed will be classified as "ATTEMPT". Attempt subjects will be followed up until Pre-Discharge. A subject ID is created by Medidata Rave upon entering the subject in the eCRF. For Attempt subjects, all applicable case report forms must be completed. If applicable, an Adverse Event eCRF form must be completed. Attempt subjects do not count towards the enrollment ceiling and will not be used for analyses of the endpoints. The original signed Informed Consent must be maintained in the center's patient file.

Treatment

A subject who had encircling of the 4 PVs (2 PV pairs) completed will be classified as "TREATMENT". These subjects are followed in accordance with the follow-up schedule and included in all study analyses. A subject ID is created by Medidata Rave upon entering the subject in the eCRF. For Treatment subjects, all applicable case report forms per the protocol must be completed. Treatment subjects do count towards the enrollment ceiling and will be used for analyses of the endpoints. The original signed Informed Consent and any relevant documentation must be maintained in the center's patient file.

It is the investigational sites's responsibility to list all Consent Ineligible, Intent, Attempt and Treatment subjects on the Screening and Enrollment Log.

11. Study Methods

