11.5.2. Procedural information

In order to avoid potential bias, the number of ablating physicians performing the index procedure and the month 3 assessment per investigational site is restricted to 2. Boston Scientific will therefore authorize maximum 2 ablating physicians per site.

Prior to starting the ablations, Rhythmia HDx + IntellaMap Orion will be used to collect an electroanatomic map (i.e. activation and voltage map) of the Left Atrium.

For all subjects it is preferred that all maps are acquired during pacing from the Coronary Sinus.

11.5.2.1. PVI ablation(s) - Ablating physician blinded to the DirectSense technology during initial encircling of PVs

It is recommended to limit the space between the center of 2 lesions to a maximum of 5 mm. The ablating physician is encouraged to avoid jumps between anatomical locations.

For the PVI ablation(s) the following information will be collected:

- Information related to PVI ablation(s):
 - o method of access to left atrium for ablation catheter, if applicable (transseptal, retrograde, or both);
 - type of PVI ablation application(s) (e.g. point (focal) lesions, dragging lesions*);
 - *The usage of dragging lesions for encircling the PVs will result in a Protocol Deviation. Dragging lesions or other types of applications are allowed for other arrhythmia(s)/additional lines.
 - specific PVI ablation technique(s) (WACA + information on additional lines if applicable)
 - o anatomical segments targeted for ablation (please refer to **Figure 11.5-2** for the 8 circumferential positions around each PV pair)
 - **Not targeting all anatomical segments for ablation will result in a Protocol Deviation.

PM007 Confidential

Form/Template 90702637 Rev/Ver AH LOCALIZE protocol, document 92142978, Rev/Ver AB Page 32 of 65

- Total number of RF applications per anatomical segment for PVI ablation;
- Power and duration for each RF application (cfr. printed EP Lab Procedure Report);
- Occurrence of steam pops;
- DirectSense data collection:
 - Blood pool impedance measurements for approximately 10 s prior to the 1st RF application (reference measurement)
 - Myocardium impedance measurements for approximately 10 s prior to the 1st RF application (reference measurement)
 - o Local impedance data will be sampled approximately every 50 ms. This data will be simultaneously recorded in a digital log file by the BSC representative.

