20.1. Reportable Events by investigational site to Boston Scientific

It is the responsibility of the investigator to assess and report to BSC any event which occurs in any of following categories:

Reportable Events:

- All Serious Adverse Events;
- All Events Leading to Death
- All Thromboembolic Events
- All Procedure Related AEs
- All Rhythmia HDx mapping system, IntellaMap Orion mapping catheter and IntellaNav MiFi OI ablation catheter Device Related Adverse Events;
- All Device Deficiencies related to the study devices (Rhythmia HDx mapping system, IntellaMap Orion mapping catheter and IntellaNav MiFi OI ablation catheter);
- Unanticipated Adverse Device Effects/Unanticipated Serious Adverse Device Effects previously not defined in the physicians manuals.

Whenever possible, the medical diagnosis should be reported as the Event Term instead of individual symptoms.

If it is unclear whether or not an event fits one of the above categories, or if the event cannot be isolated from the device or procedure, it should be submitted as an adverse event and/or device deficiency.

Death should not be recorded as an AE, but should only be reflected as an outcome of one (1) specific SAE (see **Table 20.2-1** for AE definitions).

If an additional ablation procedure is required, this additional ablation procedure should not be considered as an Adverse Event, unless associated with subject worsening condition or a new diagnosis. If the investigator considers this event to be related to any procedure, the event needs to be reported. In this case, the additional ablation procedure should be reported

in the Adverse Event eCRF as corrective action of the specific Procedure Related Adverse Event reported for the worsening condition or new diagnosis.

If the patient experiences a new arrhythmia between the index procedure and the end of study, and the investigator considers this Adverse Event to be procedure related, it needs to be reported. Refer to DFUs for the known risks associated with the study device(s).

The Boston Scientific Medical Safety group will provide safety oversight by reviewing and classifying individual events that are reported to the sponsor. Routine aggregate safety reviews will be conducted to ensure subject safety.

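### Subjects stopped after left-atrial mapping but before the first RF application are classed INTENT, so later events have no scheduled check and the exposure is not captured in the eCRF

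*Combined protocol and SAP*

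**What the plan says.** Section 10.3 defines INTENT as a consented, eligible subject who withdraws or is withdrawn "prior to starting the encircling of the 4 PVs (prior to the 1st RF application in the left atrium"; the same class takes subjects with no ablation procedure within 60 days of consent. For the whole class it states "There are no Follow Up requirements for Intent subjects" and "No index procedure eCRF must be completed". The required forms are enrollment, baseline and end of study, with one addition: "If applicable, an Adverse Event eCRF form must be completed".

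ATTEMPT, in the same section, starts at the first left-atrial RF application. All applicable case report forms are required, and "Attempt subjects will be followed up until Pre-Discharge".

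Section 11.5.2 gives the order of work: "Prior to starting the ablations, Rhythmia HDx + IntellaMap Orion will be used to collect an electroanatomic map" of the left atrium.

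Three other sections bear on the point:
- Section 20.1 lists the reportable events, among them "All Procedure Related AEs", device-related events and device deficiencies, without regard to subject class.
- Section 10.2 says "Additional data may no longer be collected after the point at which a subject has been withdrawn from the study".
- Section 12.2.1 plans additional analyses of all enrolled subjects by the section 10.3 classes.

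**The concern.** INTENT is handled as a class that was never exposed, but its boundary is the first RF application and not the start of the procedure. Between the two lie vascular and left-atrial access and a map made with two study devices, the Rhythmia system and the Orion catheter. The protocol treats mapping as carrying risk: section 19.1 applies one list of anticipated events to both the index ablation and the month 3 reassessment, which is mapping with ablation only if needed.

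At stake is the descriptive safety record for access and mapping. A complication that shows itself some hours or days after a stopped procedure could go unrecorded. Separately, the number of subjects exposed to access and mapping could not be counted from the clinical database.

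**Working it through.** No arithmetic applies. The documents give no expected number of procedures stopped before RF and no complication rate for access or mapping. The check is to follow one subject through the sections.

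**1. Which class applies.** The subject has been mapped with Orion and the procedure is then stopped. ATTEMPT needs a first RF application, so INTENT is the only class that fits. Section 11.5.2 requires the map but does not mention sheaths. That access comes first is an inference, supported by section 11.5.2.3, which starts procedure time at insertion of the first access sheath.

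**2. What each class must supply.**

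| Situation | Class | Index procedure eCRF | Scheduled check after the procedure | AE form |
|---|---|---|---|---|
| Never reached the laboratory | INTENT | No | None | If applicable |
| Stopped during access or mapping, no RF | INTENT | No | None | If applicable |
| Stopped after first RF, encircling incomplete | ATTEMPT | Yes | Pre-discharge | If applicable |

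The first two rows are identical although the exposure differs. The last two differ although both subjects had access and mapping. The protocol gives no reason for placing the dividing line there.

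**3. What happens to an event, by when it appears.**
- *Before the subject is closed out:* it is reportable under sections 10.3 and 20.1. Section 10.2 asks for full information on ongoing reportable events up to withdrawal. There is no gap in the duty to report.
- *After the procedure is stopped but before close-out:* it is reportable if the site learns of it, but no visit is scheduled at which the site would ask. The protocol does not say how soon the end-of-study form may be completed, and nothing makes it wait for discharge.
- *After withdrawal:* section 10.2 says further data may no longer be collected. Where withdrawal is for device safety or performance problems, the investigator asks permission to follow the subject, but outside the study.

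**4. Device deficiencies.** Section 20.1 makes these reportable, and Table 20.4-1 assigns them their own eCRF. The INTENT form list names the adverse event form but not the deficiency form. The end-of-procedure assessment of events and deficiencies in section 11.5.2.3 belongs to the index procedure data that INTENT subjects do not supply.

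**5. Whether exposure can be recovered from the database.** Device identification, left-atrial access approach and heparin use (section 11.5.1) and procedure time (section 11.5.2.3) are index procedure data. Without that eCRF, an exposed INTENT subject with an event might be recognised from the adverse event form. An exposed subject without an event looks like one who never attended, unless the withdrawal reason happens to show otherwise. The numerator may be known, but the denominator is not.

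**6. Effect on the main analysis.** INTENT subjects do not count towards the 60 and are not used for the endpoints. The primary endpoint and sample size do not change.

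**The case against.** The strongest reply is that adverse events are already covered. The INTENT paragraph requires an adverse event form where one applies. Section 20.1 makes no exception for the class, and Table 20.4-1 runs reporting of serious events, serious device effects and deficiencies to the end of the study. Section 10.2 adds that open reportable events are to be resolved or recorded as chronic. A complication that itself stops the case is known at once and must be reported. Section 16 requires records of the system, software version and catheters used, with dates, and section 13.2 has case data exported when the case ends. The plan has no safety endpoint, and section 12.2.1 does not drop INTENT subjects from the additional analyses. All devices are market-released.

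Most of this stands, and it rules out two stronger readings. A reader might infer that harms from access and mapping go uncollected in general; sections 10.3 and 20.1 require any event known before closure to be reported. A reader might also infer that a stopped procedure leaves no trace; only the eCRF procedure page is missing, while the device records and case export remain.

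The reply does not reach the narrower gap. A duty to report does not create an occasion to look. The reporting period in Table 20.4-1 sits beside the section 10.2 bar on data after withdrawal, and the protocol does not say which governs here. The device records kept under section 16 are site records, not eCRF data. Including INTENT subjects by class does not help when the class mixes exposed with never-exposed subjects.

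**Conclusion.** The concern holds in a limited form. For a subject whose procedure is stopped after access or mapping and before RF, events that appear later have no scheduled assessment and may not be collected after withdrawal. The eCRF also cannot distinguish this subject from one who was never exposed, so descriptive rates for access and mapping events lack a proper denominator.

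The size is unknown and could be zero. The first gap matters only if at least one subject is stopped in this window and withdrawal is recorded before a late event comes to light; the protocol fixes no date for that. The second arises with any such subject. A reader might infer that a safety rate in this plan is understated by a calculable amount, or that complications are the usual reason for stopping before RF. The documents support neither: they state no safety rate, no denominator and no frequency of or reasons for stopped procedures.

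The consequence is confined to descriptive safety reporting. The change is still worth making, because the weaker capture follows from a stated rule and is cheap to remove.

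**What to change.** Amend section 10.3 so that data requirements depend on whether the procedure started, using the first access sheath insertion that section 11.5.2.3 already takes as the start of procedure time. For every subject past that point who received no left-atrial RF, require ATTEMPT-level data:
- the index procedure eCRF, as far as it applies;
- an assessment of adverse events and device deficiencies, naming the deficiency form;
- the pre-discharge visit, completed before the end-of-study form.

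Keep these subjects outside the enrollment ceiling and the endpoint analyses. In section 12.2.1, define a safety set of all subjects with a started procedure and use it as the denominator for descriptive procedure- and device-related events.

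The cost is a wording change, plus existing eCRF pages and an existing visit for what is likely to be a small number of subjects. The 60-subject target, the primary analysis and the subjects' treatment are unchanged.
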